3.1.2 Sample Size

A literature search of metal and or plastic stenting for treatment of benign biliary strictures secondary to chronic pancreatitis yielded 4 articles representing 70 subjects treated with metal stenting (MS)²⁻⁷ and 3 articles representing 60 subjects treated with plastic stenting (PS)⁸⁻¹³.

The following meta-analysis was conducted of the probability of stricture resolution:

- Metal Stenting: A meta-analysis of the stricture resolution rate during the reported follow-up after initial stent placement yields a proportion of 0.762 [95% CI: 0.593 0.895]²⁻⁷.
- Plastic Stenting: A meta-analysis of the stricture resolution rate during the reported follow-up after initial stent placement yields a proportion of 0.611 [95% CI: 0.311 0.870] ⁸⁻¹³.

The sample size was calculated for a one-sided 0.050 Farrington-Manning test using SAS 9.2®. If the P value from the Farrington-Manning test is <0.05 then the metal stent group will be considered non-inferior to the plastic stent group. The expected probability of a stricture resolution in the metal stent arm and plastic stent arm is 66.0%, which was taken from the 95% CIs from the meta-analysis above. The non-inferiority margin (Δ) is 20%. Given these assumptions, and a one-sided 5% significance level, 2 x 74 = 148 subjects will provide 80% power to reject the null hypothesis, that the metal stent group is inferior to the plastic stent group. To compensate for possible loss of subjects between enrollment and complete assessment of inclusion/exclusion criteria and subsequent randomization, an additional 10% of subjects will be enrolled for a total of 2 x 82 = 164.

Version AA March 20, 2013 Boston Scientific WallFlex Biliary FC CP RCT SAP 90913894/Ver. AA Page 8 of 13

3.1.3 Statistical Methods

Eligibility of Subjects, Exclusions, and Missing Data

The distribution of prognostic factors between patients with and without data will be examined. Statistical models that account for censored data will be employed in appropriate circumstances, e.g. for time-to-event outcomes.

For calculating the rate of stricture resolution at 24 months after initial stent placement, patients with insufficient follow-up will be excluded from the calculation; that is, only patients that have at least follow-up through 24 month visit will be included. Sensitivity analyses, such as a tipping point analysis will be performed to assess the impact of the missing data, if the data support such analysis.

When calculating rates of adverse events, missing and partial dates will be handled as follows:

Partial Date Description	Action Taken	
Entire onset date is missing	The procedure date will be used for the	
	onset date.	
The month and the day of the month are	January 1 will be used for the month and	
missing but the year is available	day of the onset date. However, if the	
	imputed date falls before the procedure	
	date, then the procedure date will be used	
	for the onset date.	
Day is missing, but the month and year are	The 1 st will be used as the day of the onset	
available	date. However, if the imputed date falls	
	before the procedure date, then the	
	procedure date will be used for the onset	
	date.	

Baseline Comparability

Baseline data will be analyzed to assess the comparability of the treatment groups. Patient demographics, clinical history, risk factors, and procedure characteristics will be summarized using descriptive statistics (mean, standard deviation, n, minimum, maximum) for continuous variables and frequency statistics for discrete variables. Statistical testing will be performed using appropriate methods.

Post-Procedure Endpoints

The treatment effect due to important prognostic factors at the baseline level for both groups will be assessed using the logistic regression model for categorical outcomes, analysis of covariance model for continuous outcomes, or stratified methods, as appropriate.

Version AA March 20, 2013 Boston Scientific WallFlex Biliary FC CP RCT SAP 90913894/Ver. AA Page 9 of 13 Overall safety and effectiveness will be reported based on patients with sufficient followup by Metal Stent Arm and Plastic Stent Arm using the logistic regression or analysis of covariance model adjusted for baseline covariates. The Kaplan-Meier product-limit method will also be used to estimate event-free rates for time-to-event outcomes and compared using log-rank and Wilcoxon tests. Additional analyses will be performed as appropriate.

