Follow-Up Schedule	
 • Baseline: Subject screening, enrollment, LFTs and symptoms. • Study Treatment Procedure: 
 ○ Group A (MS): Stent Placement ○ Group B (PS): Stent Placement: Two or more 8.5 Fr. or 10 Fr. PS whenever possible • 1 Month Follow-up: 
 ○ Group A (MS): LFTs and symptoms ○ Group B (PS): LFTs and symptoms • Stent Exchange Follow-up: 
 ○ Group A (MS): None ○ Group B (PS): Month 4 and Month 8 • Stent Removal: 
 ○ Group A (MS): Removal at Month 12, LFTs and symptoms ○ Group B (PS): Removal of last stents at Month 12, LFTs and symptoms • Post-Stent Removal Follow-Up 
 ○ Group A (MS): Month 24 – LFTs and symptoms ○ Group B (PS): Month 24 – LFTs and symptoms • Additional ERCP visits as needed 
Note: Recurrent strictures will be treated with a metal stent in Group A (MS) and with plastic stents in Group B (PS) – no cross-over. Re-stenting after the per-protocol 12 month stenting period will be considered primary endpoint failures. Follow-up, however, will continue until Month 24 after initial stent placement for all subjects, in order to assess all secondary endpoints in a comparative fashion for the

	MS and PS arms.
Key Inclusion Criteria	
 • Age 18 or older • Willing and able to comply with the study procedures and provide written informed consent to participate in the study • Chronic pancreatitis • Symptomatic bile duct stricture (defined by cholangitis or persistent jaundice for at least one month or cholestasis associated with at least 3 times normal alkaline phosphatase levels) documented at time of enrollment for naïve stricture or at the time of prior plastic stent placement in strictures that had one prior plastic stent inserted.¹² • Common bile duct stricture based on imaging assessment of dilatation of the common and/or intrahepatic bile ducts

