We wish to demonstrate that the rate of stricture resolution using the metal stent approach is non-inferior compared to the plastic stent approach.

8.3. *Eligibility of Subjects, Exclusions, and Missing Data*

Handling of dropouts and missing data will depend on their frequency and the nature of the outcome measure and will be analyzed per the SAP (Statistical Analysis Plan).

8.4. *Analysis Populations*

8.4.1. **Enrolled Cohort**

A subject is considered “enrolled” after signing the study-specific ICF. Subjects who sign the ICF but subsequently do not meet one or more of the selection criteria will be considered screen failures and excluded from the study.

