4 GENERAL STATISTICAL METHODS

4.1 Analysis Sets

Primary endpoint and selected secondary endpoints will be done for the following cohorts.

Enrolled Cohort

A subject is considered "enrolled" after signing the study-specific ICF. Subjects who sign the ICF but subsequently do not meet one or more of the selection criteria will be considered screen failures and excluded from the study.

Intent-to-Treat Cohort (ITT)

This cohort consists of those "enrolled" subjects who meet all inclusion/exclusion criteria and are subsequently randomized. Subjects in this cohort who do not receive a study stent(s) will be counted towards the enrollment ceiling. Any adverse events occurring or resulting from a treatment attempt will be collected. Protocol deviations will be collected as necessary.

Per-Protocol Cohort (PP)

The per-protocol cohort is a subset of the ITT subjects who receive the study stent(s) as randomized and no major protocol deviations (Per ICH E9).

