7.3 Rules and Definitions

Binary event rates (proportions) will be reported on a per patient basis.

The last follow-up date will be the latest of the following dates for each patient: date of an adverse event, index procedure date, follow-up visit date, any stent or ECRP procedure date, stent removal date, and device event date.

Stricture resolution at 24 months is defined by the following two criteria being met:

• Absence of re-stenting after the per-protocol stenting period through the 24 month visit

Version AA March 20, 2013 Boston Scientific WallFlex Biliary FC CP RCT SAP 90913894/Ver. AA Page 12 of 13 • Absence of cholestasis at the 24 month visit, defined as alkaline phosphatase level not exceeding 2 times the level at completion of the per-protocol stenting period

Primary endpoint failures are 1) subjects who are re-stented during follow-up after the per-protocol stenting period and 2) subjects who have not been re-stented at month 24 but have alkaline phosphatase level exceeding 2 times the level at completion of the per-protocol stenting period.

Subjects who experience early stent removal or complete distal stent migration without subsequent re-stenting will not be considered failures. If re-stenting occurs, but the cumulative stenting period does not exceed 12 months, the subject remains eligible for primary endpoint assessment.

For the final tables, two-sided exact tests will be done to test for differences between the two groups for removability and AEs. A one-sided non-inferiority Farrington-Manning test will be done to see if stricture resolution is non-inferior in the Metal group compared to the Plastic group. A two-sided student's t-test will done to test for differences between the two groups for the number of ERCP procedures done.

Version AA March 20, 2013 Boston Scientific WallFlex Biliary FC CP RCT SAP 90913894/Ver. AA Page 13 of 13

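### The primary-rate rule in SAP 3.1.3 drops a subject who has already failed by re-stenting and is then lost before month 24

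*SAP*

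**What the plan says.** **Who enters the rate.** SAP 3.1.3, under missing data, excludes patients with insufficient follow-up from the 24-month rate and then says what sufficient means: "only patients that have at least follow-up through 24 month visit will be included". Its later paragraph on post-procedure endpoints repeats the restriction for overall safety and effectiveness, which "will be reported based on patients with sufficient followup by Metal Stent Arm and Plastic Stent Arm".

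**What counts as failure.** SAP 7.3, in the same terms as Protocol 4.1.2, states: "Primary endpoint failures are 1) subjects who are re-stented during follow-up after the per-protocol stenting period". The second type of failure is an alkaline phosphatase level at month 24 above twice the level at the end of stenting. There is one exception to the first type: if the "cumulative stenting period does not exceed 12 months, the subject remains eligible for primary endpoint assessment". The Protocol Synopsis agrees: "Re-stenting after the per-protocol 12 month stenting period will be considered primary endpoint failures".

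**Other relevant text.** SAP 4.1 says "Primary endpoint and selected secondary endpoints will be done for the following cohorts" and defines the ITT cohort as eligible randomized subjects, with no separate rule on the denominator. Protocol 8.3 states "Handling of dropouts and missing data will depend on their frequency and the nature of the outcome measure" and leaves the method to the SAP. A tipping-point analysis is planned only if the data allow it.

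**The concern.** The two SAP sections give different answers for one kind of subject. Take someone stented for the full 12 months, re-stented at month 15, and lost at month 18. SAP 7.3 needs nothing further to call this a failure, because only the alkaline phosphatase criterion requires a month-24 value. SAP 3.1.3 still takes the subject out of both numerator and denominator.

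Removing a known failure raises the observed rate in that arm. Losing metal failures favours non-inferiority, and losing plastic failures works against it. The trial has one confirmatory test and is not blinded, so unequal loss after re-stenting cannot be ruled out. If the conflict is left open, the denominator may be settled after results are seen.

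**Working it through.** **1. Does any other text restore the subject?**
- ITT (SAP 4.1): defines the cohort, but 3.1.3 then restricts the calculation.
- Kaplan-Meier (SAP 3.1.3): applies to time-to-event outcomes, not to the primary proportion.
- Tipping point (SAP 3.1.3): a conditional sensitivity analysis for missing data, and this outcome is not missing.
- Protocol 8.3: defers to the SAP.
- Last-follow-up date (SAP 7.3): the latest of several event and visit dates. It may keep in a subject who missed the visit but has a late enough date. It does not help one whose last date falls before the visit.

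The conflict remains, for a narrowed group. Where cumulative stenting time is unknown after loss, status is undetermined and there is no conflict.

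**2. The plan's own figure.** Inputs from SAP 3.1.2: 66% in both arms, margin 0.20, one-sided 0.05, 80% power. The restricted estimates are 0.547 and 0.747, so the null standard-deviation term is √(0.547×0.453 + 0.747×0.253) = 0.661 and the alternative term is √(2×0.66×0.34) = 0.670. Then

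n = [(1.645×0.661 + 0.842×0.670)/0.20]² ≈ 68.2, that is 69 per arm.

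The stated 74 gives 82.8% power, so it is not reproduced but is conservative. The inflation 74×1.10 = 81.4 gives 82, as stated. Nothing below depends on the 74.

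**3. Effect near the margin.** The Farrington-Manning statistic, with the null at a metal-minus-plastic difference of −0.20, is

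z = (p̂M − p̂P + 0.20) / √[p̃M(1−p̃M)/nM + p̃P(1−p̃P)/nP],

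where p̃ are the maximum-likelihood estimates under p̃M = p̃P − 0.20. For 47/82 v 54/82, p̃ = 0.510 and 0.710, so z = (0.5732 − 0.6585 + 0.20)/0.0745 = 1.538 and p = 0.0620. The counts are illustrative assumptions.

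| Metal | Plastic | Known failures dropped | p | Non-inferior? |
|---|---|---|---|---|
| 47/82 | 54/82 | none | 0.0620 | no |
| 47/80 | 54/82 | 2 metal | 0.0425 | yes |
| 47/80 | 54/80 | 2 in each arm | 0.0665 | no |
| 48/82 | 54/82 | none | 0.0440 | yes |
| 48/82 | 54/80 | 2 plastic | 0.0690 | no |
| 48/80 | 54/80 | 2 in each arm | 0.0471 | yes |
| 54/82 | 54/82 | none | 0.0031 | yes |
| 54/82 | 54/73 | 9 plastic | 0.0499 | yes |
| 54/82 | 54/72 | 10 plastic | 0.0658 | no |

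Two subjects from one arm can change the conclusion in either direction. Two from each arm do not. At equal observed rates, ten one-sided removals are needed.

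**4. False non-inferiority under the SAP rule.** Exact enumeration at true rates of 46% v 66%, 82 per arm. Assumed: 70% of failures are known before month 24, and only those are lost. With no loss the rate is 5.7%. With 20% lost in both arms it is 5.8%. With 10% metal and 5% plastic lost it is 6.7%, and 4.2% when reversed. The 10%/5% case removes on average 82×0.54×0.7×0.10 = 3.1 metal and 82×0.34×0.7×0.05 = 1.0 plastic failures.

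**5. Loss unrelated to outcome, and the remedies.** Simulation at the same true rates. Assumed: random loss spread over months 0–24, 20% metal and 5% plastic, with 70% of failures by re-stenting. Ranges are over separate runs.

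| Method | False non-inferiority |
|---|---|
| SAP completers rule | 4.6% to 5.1% |
| Count known failures, drop other lost subjects | 4.1% |
| Also impute the rest from never-re-stented completers | 10.9% to 11.4% |
| Also impute the rest from same-arm subjects not yet re-stented at the time of loss | 4.9% |

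The third method fails because subjects lost early may still be re-stented later. Success among never-re-stented metal subjects is 0.46/(0.46 + 0.54×0.30) = 74%, against a true 46%. Across the loss settings checked, the time-conditioned method gave 4.9% to 5.3%. At 66% in both arms with 10% loss, its power was about 84% against 83% under the SAP rule.

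**The case against.** **The group is small.** Protocol 7.5 follows everyone to month 24, Table 1 allows that visit by telephone with local blood tests, and the last-follow-up-date rule may keep some subjects in. This stands and limits the size of the problem. It does not empty the group: Protocol 6.2 allows withdrawal at any time, and 7.5 provides for loss to follow-up. Protocol 6.2 also lets data collected before withdrawal be used, so discarding the failure is avoidable.

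**A known outcome is sufficient follow-up.** This is a sensible intention, but 3.1.3 goes on to define sufficiency by the 24-month visit.

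**Completers are treated alike, whereas counting only known failures is not neutral.** This stands. Keeping lost failures while dropping lost non-failures lowers the rate in the arm with more loss. It is why the repair needs two parts.

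**Stronger readings the documents do not support.** A reader might infer that the rule favours the metal stent or roughly doubles the error rate. With 20% metal and 5% plastic loss, the enumeration in step 4 gives 10.7%. That needs a fourfold difference between arms, confined to known failures with nobody else lost, and reversing the arms gives 2.6%. No document supports either pattern. A reader might also infer that the plan makes no allowance for loss after randomization. SAP 3.1.2 does tie the 10% to "possible loss of subjects between enrollment and complete assessment of inclusion/exclusion criteria and subsequent randomization", but Protocol 8.1 places the loss between randomization and completed eligibility assessment. The Protocol Synopsis and SAP section 1 use wording that can be read as covering later loss. No clear figure can be taken from these. Alkaline phosphatase failures are unaffected, since they are determined only at month 24.

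**Conclusion.** The conflict is real and should be repaired. As written, SAP 3.1.3 removes from the only confirmatory test some subjects whom SAP 7.3 already classes as failures. The expected effect is small and its direction unknown. It is negligible when loss is similar in both arms, and absent when loss is unrelated to outcome. It can decide the result when the trial finishes near the margin and two or so known failures are lost from one arm only. Every loss count and fraction here, and the share of failures known early, is an assumption, because the documents give no usable figure for loss after randomization. The reading of the two SAP sections does not depend on those assumptions.

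**What to change.** In SAP 3.1.3:

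1. State that a subject who is already a failure under SAP 7.3, with its cumulative 12-month exception, counts as a failure in the primary analysis whatever the later follow-up.
2. Keep subjects of undetermined status in the randomized denominator by one pre-specified method that conditions on arm and time of loss. Impute from subjects in the same arm who were still not re-stented at that time, not from those never re-stented. Include subjects with unknown cumulative stenting time, and state how deaths without re-stenting are handled. Write down the pooled non-inferiority test, for example the Farrington-Manning variance combined across imputations by Rubin's rules.
3. Report the present completers rate as a sensitivity analysis.

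Item 1 should not be adopted without item 2.

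The cost is a few sentences, some added programming, and a combined test in place of a single one. No new data are needed. The method assumes that, given arm and time, loss among subjects not yet failed is unrelated to outcome. In the check above, power was not reduced.

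### Overall safety is restricted to patients with sufficient follow-up, a term the SAP never defines for safety, and the adverse event test names no denominator, so early complications may be left out

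*SAP*

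**What the plan says.** SAP 3.1.3, under Post-Procedure Endpoints, names safety as well as effectiveness: "Overall safety and effectiveness will be reported based on patients with sufficient followup", by arm, with logistic regression or analysis of covariance adjusted for baseline covariates. It makes no exception for a patient whose event came before leaving.

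The SAP says what insufficient follow-up means in one place, the missing-data part of 3.1.3, and there for one endpoint, the month-24 stricture resolution rate: "only patients that have at least follow-up through 24 month visit will be included".

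The other text on adverse events is as follows.

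- SAP 3.1.3, dates: "When calculating rates of adverse events, missing and partial dates will be handled as follows". The table that follows imputes onset dates. It sets no denominator and no rule for dropouts.
- SAP 3.1.3, time-to-event: "The Kaplan-Meier product-limit method will also be used to estimate event-free rates for time-to-event outcomes". Adverse events are not named as such an outcome.
- SAP 4.1 defines Enrolled, ITT and Per-Protocol cohorts and no safety set. For the ITT cohort it says: "Any adverse events occurring or resulting from a treatment attempt will be collected". It runs selected secondary endpoints on these cohorts without naming them.
- SAP 7.3: "two-sided exact tests will be done to test for differences between the two groups for removability and AEs", and "Binary event rates (proportions) will be reported on a per patient basis". No analysis set is given for either.
- Protocol 8.3 leaves dropouts and missing data to the SAP. Protocol 6.2 allows data from before withdrawal to be used but does not require it.

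**The concern.** Complication rates are one of the three elements of the stated objective, and related adverse events are secondary endpoint 1. A serious stent or procedure complication can itself lead to death, withdrawal or loss to follow-up. Under Protocol 11.1 a death is recorded only as the outcome of a serious adverse event. If the sufficient-follow-up condition were read as the 24-month visit, a complication that was fatal before month 24 would therefore not appear in the adjusted safety results.

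The wording is also too loose to program in one way. One programmer could run the SAP 7.3 test on all ITT subjects and another on subjects with a 24-month visit. Both could claim to follow the SAP and yet report different complication rates. The study is not blinded, so this choice should be fixed in advance.

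**Working it through.** **Design figure.** The point depends on no figure stated in the documents. The only design number used is 82 per arm, from SAP 3.1.2: 74 × 1.10 = 81.4, rounded up to 82. SAP 3.1.2 gives that 10% for loss between enrolment and randomisation, so it is not a follow-up loss rate. The documents give no follow-up loss rate and no expected adverse event rate for this trial. All counts below are assumptions.

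**Formula.** In an arm with N subjects, let E have an event, L leave before month 24, and e of those L have had an event. The rate in all subjects is E/N, and the rate in completers is (E − e)/(N − L). The completer rate is below E/N exactly when e/L exceeds E/N, that is, when leavers have more events than the arm as a whole.

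**Illustration 1: more events with metal, every metal leaver had an event.** Assume 25/82 metal and 12/82 plastic. Plastic leavers have events at about the plastic rate: 1, 1, 2 and 2 events for 4, 8, 12 and 16 leavers. P values are from Fisher's exact test.

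| Lost per arm | Metal | Plastic | Difference (points) | p |
|---|---|---|---|---|
| none excluded | 25/82 = 30.5% | 12/82 = 14.6% | 15.9 | 0.024 |
| 4 (about 5%) | 21/78 = 26.9% | 11/78 = 14.1% | 12.8 | 0.073 |
| 8 (about 10%) | 17/74 = 23.0% | 11/74 = 14.9% | 8.1 | 0.29 |
| 12 (about 15%) | 13/70 = 18.6% | 10/70 = 14.3% | 4.3 | 0.65 |
| 16 (about 20%) | 9/66 = 13.6% | 10/66 = 15.2% | −1.5 | 1.0 |

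**Illustration 2: no difference between arms.** Assume 20/82 in each arm, 8 lost per arm, all 8 metal leavers and 2 of the 8 plastic leavers having had an event. Completers show 12/74 = 16.2% versus 18/74 = 24.3%, an apparent advantage of 8.1 points for metal that is not in the full data.

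**Control case: leaving unrelated to events.** Take Illustration 1, but let metal leavers have events at the metal rate. With 8 lost per arm, about 8 × 25/82 = 2.4, so 2, had an event. Completers show 23/74 = 31.1% versus 11/74 = 14.9%, a difference of 16.2 points against 15.9. With 4, 12 or 16 lost it is 16.7, 15.7 or 15.2 points. Excluding these subjects then does little harm.

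The harm thus depends on why subjects leave, which the documents do not let anyone predict.

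**The case against.** A reader might infer that the SAP plans a completers-only safety analysis, and that a subject with an early complication certainly drops out of the comparison between arms. The documents do not support that, for four reasons.

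- The 24-month definition opens by limiting itself to stricture resolution, and adverse event rates have their own paragraph with no follow-up exclusion.
- The between-arm test of adverse events in SAP 7.3, the summaries in SAP 5.1 and the Kaplan-Meier sentence carry no such restriction. The restriction sits in the sentence on covariate-adjusted reporting.
- The ITT cohort contains these subjects, and their events are collected. The last follow-up date in SAP 7.3 can be an adverse event date, which fits counting events up to last contact.
- The illustrations are built to show harm. Without event-related leaving, the difference hardly moves.

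All of this stands, and it limits the point to a possible exclusion of unknown size. It does not remove the point. The restricting sentence names safety, the SAP offers no other meaning for its condition, and no text assigns adverse events to the ITT cohort, to the Kaplan-Meier method or to a stated denominator.

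**Conclusion.** The point holds as a risk created by the wording. The adjusted safety analysis is restricted by a condition that is undefined for safety, and the exact test has no named set. A subject with a related event who leaves before month 24 may be excluded from either.

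The rates are understated only if leaving is related to having an event, and the comparison is distorted if that relation differs by arm. With 82 per arm and 8 lost per arm, the adverse illustrations move the difference by about 8 points: 15.9 to 8.1 in one, 0 to −8.1 in the other. The control case moves it by 0.3 points. These figures rest on assumed counts and do not predict this trial's results. The all-subject rates are counts of observed events, not full 24-month risks, because event-free leavers are not seen to month 24.

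The primary non-inferiority test and the sample size are not affected. The correction should still be made before analysis, because complications are part of the stated objective.

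**What to change.** 1. In SAP 3.1.3, remove safety from the sufficient-follow-up restriction. Keep the covariate-adjusted safety model and state that it is run on the safety set below, so that safety does not lose its adjusted analysis.
2. In SAP 4.1, add a safety set: all randomised subjects with an attempted stent placement, whatever their length of follow-up.
3. State that every related adverse event up to last contact counts, including events in subjects who later die, withdraw or are lost.
4. In SAP 7.3, name the safety set as the denominator for per-patient adverse event rates and for the exact test of adverse events.
5. Add the cumulative incidence of the first related adverse event by arm. Censor event-free subjects at the last follow-up date in SAP 7.3, and treat death without a prior related event as a competing event. The date list in SAP 7.3 does not include a date of death, so state which date is used.
6. The rate among 24-month completers may stay as a supplementary table.

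The cost is SAP wording, one analysis-set flag and one extra output. The sample size and visit schedule do not change. The drawback is unequal follow-up in the crude rate, since event-free leavers count as having no event. The time-to-event estimate addresses this and should be shown beside the crude rate.
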